18.3.1. SAFETY LABORATORY EVALUATIONS

Hematology, serum chemistry, coagulation, and urinalysis are analyzed and reported by central laboratory and sometimes by local laboratory. Results out of reference range are flagged by the performing laboratory (e.g., low, high). A full list of laboratory assessments to be included in the outputs is included in Clinical Study Protocol APD334-308 Table 7.

In general, presentations will use SI Units. Quantitative laboratory measurements reported as “ $< X$ ” or “ $> X$ ”, where X may be the lower limit of quantification (LLQ) or the upper limit of quantification (ULQ), respectively, will be converted to X for the purpose of quantitative summaries, but will be presented as recorded, i.e. as “ $< X$ ” or “ $> X$ ” in the listings. For urinalysis, only pH and specific gravity are considered as quantitative tests. If local and central laboratory assessments are available from the same day, central laboratory assessments will be used in the summary as per Section 18.3.1.

The following summaries will be provided for laboratory data:

- Value and change from Baseline by visit (for hematology, serum chemistry, quantitative urinalysis [pH and specific gravity], and coagulation)
- Incidence of abnormal values according to laboratory reference ranges by visit
- Incidence of lymphocytes $< 0.2 \times 10^9/L$, $0.5 \times 10^9/L$, or neutrophils $< 0.5 \times 10^9/L$, $1 \times 10^9/L$ at Week 52 and anytime after first dose in Study APD334-308
- Shift from end of treatment to each followup visit in incidence of lymphocytes in normal range and in incidence of lymphocytes of at least 80% percent of Baseline, by visit (2-Week Follow-Up, 4-Week Follow-Up, and Last FollowUp)Shift from Baseline to Week 52/Early Termination Visit according to laboratory reference range (for quantitative measurements and categorical measurements)
- Evaluation of Drug-Induced Serious Hepatotoxicity (eDISH) plots for the following laboratory assessments (using values after the first administration of study treatment):
 - Maximum aspartate aminotransferase (AST) versus same-day total bilirubin
 - Maximum alanine aminotransferase (ALT) versus same-day total bilirubin
 - Maximum gamma-glutamyl transferase (GGT) versus same-day total bilirubin
 - Maximum alkaline phosphatase (ALP) versus same-day total bilirubin

The eDISH plots above will be repeated with adjustment for elevated Baseline.

- Incidence of hepatic enzyme elevations by visit
 - $> 1 \times$, $2 \times$, $3 \times$, $5 \times$, $8 \times$, $10 \times$, $20 \times$ upper limit of normal (ULN) elevation in ALT
 - $> 1 \times$, $2 \times$, $3 \times$, $5 \times$, $8 \times$, $10 \times$, $20 \times$ ULN elevation in AST
 - $> 3 \times$, $5 \times$, $10 \times$, $20 \times$ ULN elevation in either ALT or AST
 - $> 1 \times$, $1.5 \times$, $2 \times$, $3 \times$ ULN elevation in total bilirubin
 - $> 1 \times$, $1.5 \times$, $2 \times$, $3 \times$, $5 \times$, $8 \times$ ULN elevation in ALP
 - $> 1 \times$, $2 \times$, $3 \times$, $5 \times$, $8 \times$ ULN elevation in GGT
 - $> 3 \times$ ULN elevation in either ALT or AST and $> 1.5 \times$ ULN elevation in total bilirubin
 - $> 3 \times$ ULN elevation in either ALT or AST and $> 2 \times$ ULN elevation in total

bilirubin

- $> 3 \times$ ULN elevation in either ALT or AST and $> 1.5 \times$ ULN elevation in ALP
- $> 3 \times$ ULN elevation in either ALT or AST in temporal association with treatment-emergent nausea, vomiting, anorexia, abdominal pain, or fatigue identified by PT, where temporal association is defined as ± 14 days of onset date from the time of elevation.

If both central and local assessments of total bilirubin are available on the same day, the central result will take precedence over the local result in the eDISH plot. If the maximum AST/ALT/GGT assessment occurs at two 2 different dates, the assessment with the higher accompanying Bilirubin value will be used. Two versions of the eDISH plots will be presented, with one showing values as multiples of upper limit of normal, and the other one showing values as multiples of upper limit of normal, or subject's baseline, whichever is higher. Subject's laboratory assessments at all timepoints will be listed in chronological order. Values outside of the laboratory reference range will be flagged. Values obtained from local laboratory will be flagged. Listing of lymphocytes and neutrophils over time in subjects ever with lymphocytes $< 0.5 \times 10^9/L$ or neutrophils $< 1 \times 10^9/L$ will also be provided.

18.3.2. PREGNANCY TESTS

Urine beta-human chorionic gonadotropin (β -hCG) and/or serum β -hCG pregnancy tests are performed throughout the study in female subjects of childbearing potential. All pregnancy test results (positive or negative) will be listed in chronological order.

18.3.3. OTHER SCREENING LABORATORY ASSESSMENTS

Screening laboratory assessments for virology, drug screen/toxicology, QuantiFERON Tuberculosis (TB) Gold, stool pathogens, and *Clostridioides difficile* (formerly known as *Clostridium difficile*) will be listed. Analyses of genetics and exploratory efficacy-related biomarkers data based on samples collected at Screening in subjects who provided consent will be described in a separate plan.

18.4. ECG EVALUATIONS

ECGs are recorded on a 12-lead ECG machine and read centrally. The following ECG parameters will be reported for this study:

- HR (bpm)
- RR Interval (msec)
- PR Interval (msec)

- QRS Interval (msec)
- QT Interval (msec)
- QTcF Interval (msec)
- Overall assessment of ECG (Investigator's judgment):
 - Normal
 - Abnormal, Not Clinically Significant (Abnormal NCS)
 - Abnormal, Clinically Significant (Abnormal CS)
- Overall interpretation of ECG (central reader):
 - Normal
 - Abnormal NCS
 - Abnormal CS
- AV conduction abnormalities
 - First-degree AV block
 - Second-degree AV block type 1
 - Second-degree AV block type 2
 - Third-degree AV block

The following summaries will be provided for ECG data:

- Value and change from Baseline by visit (for quantitative measurements)
- Incidence of markedly abnormal values (defined in [Section 18.4.1](#)) and AV blocks by visit
- Shift in normal/abnormal NCS/abnormal CS in the overall interpretation (by investigator) from Baseline to Week 52/Early Termination Visit and to the worst-case post-Baseline result
- Shift in markedly abnormal categories from Baseline to post-Baseline by visit

Listings of ECG results, including first dose cardiac monitoring, and discharge criteria for first dose cardiac monitoring will be provided.

A listing of all ECG assessments over time in subjects meeting markedly abnormal criteria will also be provided. For each subject, only ECG parameters ever meeting markedly abnormal criteria will be included.

18.4.1. ECG Markedly Abnormal Criteria

Markedly abnormal quantitative ECG measurements will be identified in accordance with the

following predefined markedly abnormal criteria:

- Absolute values in QT and QTcF:
 - ≥ 450 msec (male) or ≥ 470 msec (female) in QTcF
 - > 500 msec in QT
- Change from Baseline in QT and QTcF:
 - > 30 msec increase from Baseline
 - > 60 msec increase from Baseline

In shift tables, subjects will be classified according to the binary category for each parameter and the predefined markedly abnormal criterion (i.e., Markedly abnormal vs. Not markedly abnormal).

18.5. Vital Signs

The following vital signs measurements will be reported for this study:

- Systolic Blood Pressure (mmHg)
- Diastolic Blood Pressure (mmHg)
- Heart Rate (bpm)
- Respiratory Rate (resp/min)
- Temperature ($^{\circ}$ C)

The following summaries will be provided for vital signs data:

- Value and change from Baseline by visit
- Value and change from predose on Day 1 (as reported on the eCRF) by timepoint
 - For heart rate only, value and change from predose to minimum postdose heart rate on Day 1 will be included in the same table
- Incidence of markedly abnormal values (defined in Table 4) by visit, including anytime after first dose in Study APD334-308
- Listing of subjects meeting markedly abnormal criteria
- Incidence of minimum heart rate on Day 1 in Study APD334-302 by postdose timepoint (1, 2, 3, 4, and > 4 hours postdose, and Day 1 overall) and heart rate interval (≥ 65 , 60 to 64, 55 to 59, 50 to 54, 45 to 49, 40 to 44, < 40 bpm)
 - If minimum heart rate is attained at multiple postdose timepoints, only the earliest timepoint will be counted in this incidence summary.

- Time to minimum heart rate on Day 1 in Study APD334-302 by planned hourly timepoint (if minimum heart rate is attained at multiple postdose timepoints, only the earliest timepoint will be counted).
 - Actual time elapsed from first dose to minimum heart rate on Day 1 will also be summarized using descriptive statistics (n, mean, SD, median, minimum, and maximum) in the same table.
- Line plots for mean value and mean change from predose on Day 1 in Study APD334-302, up to 4 hours postdose by parameter and timepoint (systolic blood pressure, diastolic blood pressure, and heart rate)
- Line plots for mean value and mean change from Baseline by parameter and visit (systolic blood pressure, diastolic blood pressure, heart rate, body temperature, and respiratory rate)

Listings of all vital signs, including first dose cardiac monitoring, and discharge criteria for first dose cardiac monitoring will be provided. A listing of vital signs assessments over time in subjects meeting a markedly abnormal criterion will also be provided. For each subject, only the parameters with at least one markedly abnormal criterion satisfied will be included.

For subjects with extended monitoring or remonitoring, a listing of systolic blood pressure, diastolic blood pressure, heart rate values, and change from predose in all parameters on Day 1, Day 2, and any remonitoring visit will be provided.

18.5.1. Vital Signs Specific Derivations

- Temperature (°C) = (5/9) (Temperature (°F) – 32)

18.5.2. Vital Signs Markedly Abnormal Criteria

Markedly abnormal quantitative Vital Signs measurements will be identified in accordance with the following predefined markedly abnormal criteria:

Table 4 Markedly Abnormal Criteria for Vital Signs

Variable	Unit	Low	High
SBP	mmHg	≤ 90 mmHg	> 150 mmHg
DBP	mmHg	≤ 50 mmHg	> 90 mmHg
Heart rate	bpm	< 40 bpm < 50 bpm < 50 bpm and decrease from predose (Baseline) of > 10 bpm at 4 hours on Day 1 or Day 2 or remonitoring visit	>100 bpm

bpm, beats per minute; DBP, diastolic blood pressure; SBP, systolic blood pressure.

18.6. Physical Examination

A listing of all physical examination assessments in subjects who had at least 1 abnormal finding.

18.7. Other Safety Assessments

18.7.1. Pulmonary Function Tests

The following pulmonary function test (PFT) measurements (actual and % Predicted) will be reported for this study:

- FEV₁
- FVC
- Total Lung Capacity (TLC)
- FEV₁/FVC ratio
- Forced Expiratory Flow (FEF) 25-75
- DLCO (if available)

The following summaries will be provided for PFT data:

- Value and change from Baseline by visit
- Incidence of markedly abnormal values by visit (Section 18.7.1)

All PFT data will be listed. A listing in subjects who ever reported an abnormality in PFT will also be provided, including a flag for whether markedly abnormal criterion is also met.

18.7.1.1. PFT Markedly Abnormal Criteria

Markedly abnormal quantitative PFT measurements will be identified in accordance with the following predefined markedly abnormal criteria:

- % Predicted FEV₁ < 50%
- % Predicted FVC < 50%
- % Predicted FEV₁/FVC ratio < 50%

Potentially important PFT measurements will also be identified using the criteria below:

- Decrease from Baseline > 20% in FEV₁, ie, percent change from Baseline < -20%
- Decrease from Baseline > 20% in FVC, ie, percent change from Baseline < -20%
- Decrease from Baseline > 20% in DLCO, ie, percent change from Baseline < -20%

18.7.2. Ophthalmoscopy And Optical Coherence Tomography [OCT]

The following summaries will be provided for ophthalmoscopy and optical coherence tomography (OCT) data:

- Values and change from Baseline in central foveal thickness and intraocular pressure by visit
- Categorical results in ophthalmoscopy with OCT parameters by visit (the categories are listed on the eCRF)

Only PFT and OCT assessments completed by 50 or more subjects in the Safety Set will be presented in the summaries.

A listing of all ophthalmoscopy and OCT assessments will be provided. A listing of subjects who ever reported an abnormality in OCT will also be provided. Additionally, a listing of retinal photograph and eye pressure assessments will be provided for subjects who experienced an AE related to eye disorders.

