The safety objective is to assess the long-term safety of etrasimod in Japanese subjects with moderately to severely active UC after daily doses of 2 mg for up to 52 weeks (12 weeks in Study APD334-302 plus 40 weeks in Study APD334-308).

CCI

Study design:

This is a multicenter, double-blind, placebo-controlled extension study of APD334-302 (12-week, randomized, double-blind, placebo-controlled induction study) to evaluate the efficacy and safety of etrasimod 2 mg in Japanese subjects with moderately to severely active UC. Study APD334-308 consists of a 40-Week Treatment Period and a 4-Week Follow-Up Period.

Japanese subjects who completed the Week 12 visit of Study APD334-302 are eligible for the APD334-308 study. The Week 12 visit of Study APD334-302 serves as the Day 1 visit of Study APD334-308. Subjects will continue with the same blinded treatment assigned in Study APD334-302 for a total treatment duration of 52 weeks (12 weeks in Study APD334-302 plus 40 weeks in Study APD334-308).

End of 40-Week Double-Blind Treatment Period

Disease worsening will be monitored by Investigators through the Treatment Period. Subjects who either experience disease worsening or complete all study procedures at Week 52 will have the option to enroll into the APD334-303 open-label extension (OLE) study if they meet all eligibility criteria. Subjects may be eligible to enroll in the OLE study provided their endoscopic score (ES) is > 2 and they meet one of the following entry criteria:

- Rectal bleeding (RB) subscore ≥ 2 at 2 timepoints at least 7 days and no more than 14 days apart
- RB + stool frequency (SF) subscore ≥ 4 at 2 timepoints at least 7 days and no more than 14 days apart
- RB subscore \geq 2 or RB + SF subscores \geq 4 (in any order) at 2 timepoints at least 7 days and no more than 14 days apart

For subjects discontinuing prior to Week 52, an endoscopic evaluation is required to confirm eligibility for the OLE study. An endoscopy should be performed upon the appearance of UC symptoms but no more than 14 days after the second timepoint for entry criteria above.

A proctosigmoidoscopy does not need to be repeated if performed within the last 4 weeks. Subjects who do not participate in the OLE study will have 2-Week and 4-Week Follow-Up visits after their last on treatment visit/Early Termination visit.

Number of subjects (planned):

Approximately 35 Japanese subjects are planned to be enrolled into this study.

Eligibility criteria:

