10.12.2. Safety Analysis

All safety data will be listed and summarized by treatment group. All TEAEs will be coded using the latest version of MedDRA and tabulated by System Organ Class and Preferred Term. Incidence of adverse events, SAEs, and adverse events leading to discontinuation will be summarized and presented in descending order of frequency. Associated laboratory parameters such as hepatic enzymes, renal function, and hematology values will be grouped and presented together. Individual subject values will be listed and values outside of the standard reference range will be flagged. Shift tables and analyses of changes from baseline will be produced. The change from baseline for each of the vital signs and 12-lead ECG parameters will be summarized. Incidence of abnormal vital signs parameters and outlier 12-lead ECG results will be tabulated.

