5.6. SAFETY SET

The Safety Set will include all subjects who receive at least 1 dose of study treatment in Study APD334-308. For this set, subjects will be analyzed according to the treatment received, regardless of randomization. The Safety Set will be used for all safety analyses.

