6.5. Statistical Tests

Due to the limited number of subjects anticipated to enroll in this study and central randomization not designed to control for allocation ratio in Japan. Point estimate with 95% confidence intervals (CIs) and nominal p-values (2-sided) will be reported.

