7. DETERMINATION OF SAMPLE SIZE

There is no formal sample size estimation for Study APD334-308. The number of subjects to be enrolled in this study was determined by number of Japanese subjects enrolled in Study APD334-302, and those subjects were eligible to enroll according to Study APD334-308 protocol.

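### The SAP's 50-subject minimum for PFT and OCT summaries cannot be met at the planned enrolment of about 35, so the tables it specifies would not be presented

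*SAP*

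**What the plan says.** For lung function, SAP 18.7.1 states "The following summaries will be provided for PFT data". It then names levels and changes from baseline at each visit, and the incidence of markedly abnormal values at each visit. Six parameters are covered (FEV1, FVC, total lung capacity, FEV1/FVC, FEF 25-75 and, where available, DLCO), each as the actual value and as percent predicted.

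For the eye assessments, SAP 18.7.2 states "The following summaries will be provided for ophthalmoscopy and optical coherence tomography (OCT) data". It names central foveal thickness, intraocular pressure and the categorical ophthalmoscopy/OCT results.

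After the second list, SAP 18.7.2 adds: "Only PFT and OCT assessments completed by 50 or more subjects in the Safety Set will be presented in the summaries".

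Three other places fix how many subjects can count:
- SAP 5.6: "The Safety Set will include all subjects who receive at least 1 dose of study treatment in Study APD334-308".
- Protocol synopsis, number of subjects: "Approximately 35 Japanese subjects are planned to be enrolled into this study".
- SAP 7, which gives no formal calculation: "The number of subjects to be enrolled in this study was determined by number of Japanese subjects enrolled in Study APD334-302".

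Protocol 10.12.2 sets the general expectation: "All safety data will be listed and summarized by treatment group".

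**The concern.** The SAP specifies a set of tables and then sets a condition for showing them that the planned study cannot satisfy. A programmer who follows the text would produce no PFT tables and no OCT tables.

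The restriction does not look like a deliberate small-sample choice. Elsewhere the SAP explains when small numbers change the plan: section 3.3 drops the stratified CMH analysis and section 5.4 drops the Per Protocol analyses, both with reasons. The 50-subject rule has no rationale and is not in section 3.3. Laboratory, ECG and vital-sign data from the same subjects (SAP 18.3 to 18.5) are summarized with no minimum count.

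The protocol lists PFT, ophthalmoscopy and OCT among its safety assessments, and section 1.3 ties the lung and eye monitoring to the mechanism of action. The safety objective is long-term safety in Japanese subjects. At stake are the by-arm tables of mean change (for example FEV1, FVC, DLCO and central foveal thickness) and of the incidence of markedly abnormal PFT values.

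**Working it through.** There is no sample-size formula to reproduce, because SAP 7 states that none was used. The check compares the largest possible count with the threshold.

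**Inputs**
- Threshold: 50 subjects (SAP 18.7.2).
- Planned enrolment: about 35 (protocol synopsis). Protocol 10.2 gives the same figure for the Japanese subjects in the parent study, who are the only source of subjects.
- Safety Set: subjects dosed in APD334-308 (SAP 5.6), so no larger than the number enrolled.

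**Step 1: how the count is taken.** The sentence could be read per visit, per parameter, or as ever completed during the study. Each is a count of Safety Set members, so each is at most about 35. The choice of reading does not matter.

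**Step 2: the gap**
- Shortfall: 50 − 35 = 15.
- Share of the threshold: 35/50 = 70%.
- Overrun needed with every assessment complete: 15/35 = 43%.

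**Step 3: allowing for missing assessments.** The documents give no missing-data rate, so the rates here are assumed. Enrolment needed for 50 completers at one visit is 50/(1 − m), rounded up:

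| Assumed missing, m | Enrolment needed | Over plan |
|---|---|---|
| 0% | 50 | 43% |
| 10% | 50/0.9 → 56 | 60% |
| 20% | 50/0.8 → 63 | 80% |
| 30% | 50/0.7 → 72 | 106% |

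**Step 4: cells that are smaller still.** Under protocol Table 7, the Week 32 PFT is required only for subjects with a history of mild pulmonary disease. The 2-Week Follow-Up PFT and OCT are required only after an abnormal Week 52/Early Termination result. DLCO is measured only at sites that have it (protocol 9.8.4).

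**Step 5: what the rule covers.** On the PFT side it covers 6 parameters × 2 scales = 12 measures, with both the change and the incidence tables. On the eye side it covers the OCT tables. Intraocular pressure and stand-alone ophthalmoscopy findings are arguably outside the words used, and might survive.

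**The case against.** The strongest reply has four parts.

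**It is a display filter, not a contradiction.** A general promise of tables followed by a condition on which ones appear can be read as consistent. Whether the output is empty also depends on actual enrolment, which the documents do not give. This is fair as far as it goes: 35 is a plan, not a cap. But a filter that removes everything at the planned size defeats the section it sits in, and the SAP itself calls enrolment limited (sections 3.3 and 8.2).

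**The table shells may settle it.** SAP 2.5 leaves the scope of analysis to the shells, and Appendix 1 says outputs follow them. The shells cannot be seen, but nothing in the SAP says that they override the threshold.

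**Little is lost.** All PFT, ophthalmoscopy and OCT data are listed without any minimum. Abnormal PFT values are flagged, so incidence by arm could be counted by hand, and means could be worked out from the listings. Macular edema and pulmonary disorders are tabulated as events of special interest (SAP 18.1.5). Reasons for stopping treatment and adverse events leading to discontinuation are also tabulated. An integrated analysis with the parent study is planned. Neither PFT nor OCT is a named safety endpoint in protocol 10.11. All of this stands, and it limits the seriousness. It does not supply the by-arm mean-change tables, for which this SAP states no substitute. The integrated analysis is in a separate plan whose PFT and OCT content cannot be seen.

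**Protocol 10.12.2 is weak support.** Its general sentence does not name PFT or OCT, and protocol 10.1 leaves details to the SAP. That is right. The point rests mainly on the SAP's own text.

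**Conclusion.** The concern holds. At the planned size of about 35, a 50-subject minimum removes all PFT summaries and the OCT summaries that SAP 18.7.1 and 18.7.2 specify. The threshold is missed by 15 subjects, and enrolment would need to exceed plan by at least 43% before any table appeared.

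This assumes that final enrolment was near plan and that the sentence is applied as written. The result does not depend on whether the count is per visit, per parameter or over the whole study. The missing-data scenarios show only how the gap widens, and the conclusion does not need them.

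The consequence is moderate: prespecified, mechanism-driven safety tables would drop out without a stated reason. Subject-level data and event tables remain, and no efficacy endpoint or named safety endpoint changes.

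**What to change.** Delete the 50-subject sentence from SAP 18.7.2 and present the tables already specified, with n in every cell. Add footnotes marking the selected subsets: Week 32 PFT, 2-Week Follow-Up PFT and OCT, and DLCO. Protocol 9.8.4 names FEV1 and FVC as the core measurements, so total lung capacity and FEF 25-75 may also be sparse and should carry a note.

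If some or all of these data are meant to be listed only, say so in section 18.7 in place of the promised tables, and record it in section 3.3 against protocol 10.12.2. A minimum count scaled to this study would also be coherent if the aim is to suppress very sparse cells, but it needs a stated reason. If outputs are already final, the missing tables can be added and identified in the study report as unplanned, as SAP 4.2 allows.

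The cost is one deleted sentence and a few footnotes. The drawback is small cells. If the 2:1 ratio held in Japan, 35 subjects would split into about 23 on etrasimod (35 × 2/3) and 12 on placebo (35 × 1/3). The SAP describes "central randomization not designed to control for allocation ratio in Japan", so the placebo arm could be smaller or larger. The tables should be read as description, and the subset cells should not be taken to represent a whole arm.
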